Global increases in sugar consumption have prompted the development of sugar substitutes, including polyols or non-fermentable sugars, of which the most commonly used are nutritive sweeteners like sorbitol and xylitol. Chewing gum is a means to administer therapeutic agents and contribute to improving oral conditions. In the national market, there are sugared chewing gums (sucrose) and sugar-free gums that include xylitol plus sorbitol. These gums are consumed in high quantities, especially by teenagers and young adults, and the few studies conducted in Ecuador indicate a significant elevation in salivary pH from 6.4 to 7.14^{7,8} after consuming sugar-free chewing gums, compared to sugared gums. However, these investigations evaluate salivary pH levels using reactive strips. Additionally, there are no locally available chewing gums solely based on xylitol, and there are also sugar-free chewing gums that use a blend of compounds as sweeteners without indicating the percentages. Therefore, high-quality randomized controlled trials are needed to determine the effectiveness on salivary pH.

A study conducted in India⁵ compared the efficacy of two sugar-free chewing gums. The first group showed a significant increase in salivary pH levels up to 2 minutes after consuming sugar-free chewing gums (pH 7.98 \pm 0.19), which gradually decreased to 7.60 \pm 0.12 at 30 minutes, compared to another group of sugar-free chewing gums where salivary pH levels at two minutes were higher (pH 7.49 \pm 0.16) than at 30 minutes (pH 6.82 \pm 0.28), showing statistically significant differences within each group. Regarding salivary flow, there was a higher average at two minutes (1.89 \pm 0.42), which gradually decreased to 1.09 \pm 0.31 at 30 minutes (1.89 \pm 0.45), which decreased to 1.04 \pm 0.31 at 30 minutes, showing statistically significant differences.

Therefore, chewing gums stimulate an increase in salivary flow, which contributes to diluting and cleaning the oral cavity, as well as buffering and allowing ionic exchange. Additionally, they promote a neutral or alkaline salivary pH level, which may contribute to enamel remineralization and, therefore, prevent dental caries.² Furthermore, they could serve as a complement to oral hygiene in situations where tooth brushing is not possible.

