Based on the above, the following question is raised: Does the consumption of xylitol-based chewing gums positively influence salivary flow and pH compared to sugared or sugar-free gums?

JUSTIFICATION

This research is focused on determining the effects of xylitol-based chewing gums (100% xylitol, Xylichew brand), sugarfree gums (sorbitol, maltitol, mannitol, and xylitol, Trident brand), and sugared gums (sugar, dextrose, glucose, sweeteners such as aspartame and acesulfame-K, Agogó brand) on salivary flow and pH in young adults: a randomized controlled trial in students of the Dentistry Career at the Catholic University of Cuenca, 2023. In our context, the distribution of sugar-free gums includes xylitol and sorbitol among its ingredients, without indicating the exact proportions of each. Additionally, there are no chewing gums in the Ecuadorian market that contain xylitol as the sole ingredient, hence the need to compare with a foreign chewing gum, which indicates the presence of only xylitol.

Vantipalli et al.⁵ showed statistically significant differences between two sugar-free chewing gums in terms of unstimulated salivary pH and salivary pH stimulated at 2 minutes, showing an increase at this time compared to 30 minutes after gum consumption. Similar results were reported for salivary flow, showing a higher flow at two minutes compared to 30 minutes after gum consumption. This study demonstrates significant changes within each group and between subgroups for salivary pH levels, while salivary flow showed significant changes only within each gum group evaluated.

This study has a degree of originality, as there are studies conducted in Ecuador that found significant changes with an increase in salivary pH levels in chewing gums containing sorbitol and maltitol. However, they did not evaluate chewing gum containing xylitol as the sole ingredient, and they used reactive strips as equipment to evaluate salivary pH. Therefore, high-quality and appropriate equipment is needed to determine salivary pH, and the Molecular Biology Laboratory has a pH meter, providing a precise tool for assessment.

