H1: The consumption of different chewing gums results in changes in the level and flow of initial salivary pH at 10, 20, and 30 minutes.

METHODOLOGY

Research Design

- It is a quantitative, analytical, experimental study conducted through a double-blind, parallel randomized controlled trial.
 - Definition of the study population and, if applicable, it is necessary to detail how the sample size calculation was performed (formulas and development).

The population will consist of all enrolled students (1275 students in the period September 2023-February 2024) in the Dentistry program at the Catholic University, aged between 18 and 25 years old, who voluntarily meet the inclusion criteria.

For the sample size calculation, an online calculator was used, employing the formula for comparing two means. A confidence level of 95% and a statistical power of 90% were set. Based on a previous study that reported a desired difference of 1 unit, with a precision and variance of 1 in the reference or control group, it was determined that 21 participants would be needed in each group. However, to account for potential information loss or dropout from the study, the sample size was adjusted by 15%, resulting in the requirement of 25 participants in each group. (Figure 1)

$$n = \frac{2\left(Z_{\alpha} + Z_{\beta}\right)^2 * S^2}{d^2}$$

Figure 1. Hypothesis testing formula for determining means.¹⁴

Replacing the formula

n= participants needed in each of the groups

 $Z\alpha = Z$ value corresponding to the desired risk 0.05 = 1.96

 $Z\beta = Z$ value corresponding to the desired risk 90%= 1.282

 S^2 = Variance of the quantitative variable in the control group =1

d= Minimum detectable difference desired = 1

$$n = \frac{2(1.96 + 1.282)^2 * 1^2}{1^2} = 20.99$$

• List of establishments where observational or intervention research will be conducted on human subjects. It is necessary to specify whether the institutions are public or private and include their postal address and letter of interest (Appendix B)

The intervention will take place among students of the Dentistry program at the University of Cuenca, main campus, in the Molecular Biology laboratory. Sampling and determination of salivary flow and pH level will be carried out there. (Appendix B)

• Inclusion Criteria

Within the selection criteria, the inclusion criteria will be participants with at least 20 teeth, providing written informed consent, and being willing to comply with the study procedures.

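### The 90% power rests on a unit-less difference of 1 and variance of 1 that match the cited spread of neither pH nor flow; read as a 1-SD target, the planned Tukey test gives about 73%

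*Protocol*

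**What the plan says.** The sample-size paragraph (Protocol, Methodology, Research Design) uses the formula for two means. On error rates it says "A confidence level of 95% and a statistical power of 90% were set". The inputs come from "a previous study that reported a desired difference of 1 unit, with a precision and variance of 1" in the reference or control group. The symbol list repeats them as "d= Minimum detectable difference desired = 1" and "Variance of the quantitative variable in the control group =1". The result, printed as 20.99, is taken as 21 per group and raised to 25 for 15% loss. No outcome, unit or time point is attached to either input, and the previous study is not identified.

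The trial has two outcomes on different scales, salivary flow and salivary pH, each measured at baseline and in three windows after chewing starts (Research Objectives; section 7.3). There are four arms. The Data Analysis Plan (section 9) compares means by ANOVA followed by Tukey's test at 0.05.

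The Research Problem section holds the only pH and flow figures with SDs, from a study in India comparing two sugar-free gums. It also cites Ecuadorian work reporting "a significant elevation in salivary pH from 6.4 to 7.14", without an SD. The Justification adds that in the Indian study pH differed between gums, "while salivary flow showed significant changes only within each gum group evaluated".

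**The concern.** A power statement means something only for a named outcome, a difference in that outcome's units and a plausible SD. Here one pair of numbers serves both pH and flow, and the variance is far from every SD that the protocol itself cites. The calculation is also for a single comparison of two means, whereas the planned inference is Tukey's test over the six pairs formed by four arms, which has a higher critical value.

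What is at stake is how the results are interpreted. A reader cannot tell from the paragraph how small a pH or flow difference the trial can detect, and may carry the 90% over to comparisons that do not have it.

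**Working it through.** **1. The protocol's own figure.** n = 2(Zα + Zβ)²S²/d², with Zα = 1.96, Zβ = 1.282, S² = 1, d = 1:
- 2 × (3.242)² = 21.02. With Zβ = 1.28 it is 20.995, which explains the printed 20.99. The gap is immaterial.
- 21/0.85 = 24.7, rounded up to 25. The arithmetic reproduces; the question is about the inputs.

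**2. Planning variance against the cited SDs (Research Problem).**

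| Outcome | Time | Cited SDs | Variances | 1 ÷ variance |
|---|---|---|---|---|
| pH | 2 min | 0.19, 0.16 | 0.036, 0.026 | 28, 39 |
| pH | 30 min | 0.12, 0.28 | 0.014, 0.078 | 69, 13 |
| Flow | 2 min | 0.42, 0.45 | 0.176, 0.203 | 5.7, 4.9 |
| Flow | 30 min | 0.31, 0.31 | 0.096, 0.096 | 10.4, 10.4 |

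The assumed variance is about 13-69 times the cited pH variances and 5-10 times the cited flow variances.

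**3. Reading A: a difference of 1 in natural units.** Take the least favourable cited SD, 0.45. The standardised difference is 1/0.45 = 2.22, and the noncentrality at 21 per arm is 2.22 × √(21/2) = 7.20. The critical values are 2.02 for one t-test (40 df) and 2.62 for Tukey (four groups, 80 df). Power exceeds 99.9% on either, and smaller SDs only raise it. Under Tukey, power for 1 unit stays at 90% or more up to an SD of about 1/1.211 = 0.83.

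**4. Reading B: a difference of 1 SD.** The noncentrality is √(21/2) = 3.24.
- Normal approximation, 21 per arm: 89.98%.
- Single two-sided t-test, 21 per arm: 88.5%.
- One pair under Tukey, four arms, 21 per arm (critical value 2.62, 80 df): 73.0%.
- One pair under Tukey, 25 per arm (noncentrality 3.54, critical value 2.61, 96 df): 81.9%.

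The Tukey figures take a one-way ANOVA at one time point with a common SD.

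**5. What 21 per arm can detect with 90% power.** Solving for the effect gives 1.025 SD for one unadjusted t-test and 1.211 SD under Tukey. Multiplying the latter by the cited SDs:
- pH: 1.211 × 0.12 = 0.15 to 1.211 × 0.28 = 0.34 units.
- Flow: 1.211 × 0.31 = 0.38 to 1.211 × 0.45 = 0.55 units.

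**6. Cited between-gum differences, for context.** pH: 7.98 − 7.49 = 0.49 at 2 min and 7.60 − 6.82 = 0.78 at 30 min. Flow: 1.89 − 1.89 = 0 and 1.09 − 1.04 = 0.05, if the flow sentence is read as giving one series per gum.

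**The case against.** Several objections have force.

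- *The planning variance errs on the safe side.* This stands. For a 1-unit difference on the cited SDs, 90% is a floor for both outcomes, even under Tukey. It is still not an accurate figure for either outcome, and it does not tell the reader what smaller differences are within reach.
- *The input is a target, and perhaps a generic 1-SD effect.* The symbol list does call d a desired difference, and n depends only on d/S, so this reading cannot be excluded. It is the reading under which the planned Tukey comparisons have about 73% power.
- *The benchmark is not this trial's comparison.* Also fair. The cited study compared two sugar-free gums, its title in the reference list says children, and its 2-minute time point lies outside this trial's windows of 5-10, 15-20 and 25-30 minutes. Contrasts with sugared gum or paraffin in adults aged 18-25 may be larger, and the SDs may differ. The flow sentence is garbled and prints no unit. The detectable differences in natural units are therefore illustrative; the 1.21 SD figure does not depend on them.

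Three stronger inferences are tempting and are not supported:

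- A reader might conclude that the trial is underpowered for flow because the cited between-gum difference is at most 0.05. The protocol never sets that as a target, and low power for a near-zero difference is not in itself a design fault.
- A reader might say that the cited data contradict the sizing study. That study is not identified, so its variance cannot be checked.
- A reader might infer that a non-significant flow result will be reported as equality. The protocol does not say so.

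**Conclusion.** The point holds as a fault in the inputs and in the power claim, not in the arithmetic or the number recruited. The variance of 1 is 5 to 69 times anything the protocol cites, so 90% describes neither pH nor flow accurately: on the cited SDs a 1-unit difference has more than 99.9% power. If a 1-SD effect was meant, the planned pairwise Tukey comparisons have about 73% power with 21 analysable per arm and about 82% with all 25, not 90%.

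The first result assumes that the cited SDs carry over to young adults and these gums. The second needs no outside SD, only approximate normality, a common SD and equal arms.

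The consequence is limited. The sample is ample for pH differences of the size cited. For flow, differences smaller than the detectable one cannot be ruled out by a non-significant result.

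**What to change.** Keep 25 per arm. In the sample-size paragraph:

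- State which outcome, in which unit, the calculation serves.
- Replace the unqualified 90% claim with the difference detectable at 90% power under four-arm Tukey with 21 analysable per arm: 1.21 SD, about 0.15-0.34 pH units and 0.38-0.55 flow units on the cited SDs.
- State as assumptions that these SDs come from two sugar-free gums in a study whose title says children, partly at a time point outside this trial's windows, and that the flow sentence needs clarifying.
- Add that a non-significant flow comparison does not rule out differences smaller than the detectable one.

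The cost is one reworded paragraph and a less favourable stated power for a 1-SD effect. No participants are added, and the analysis does not change.

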• Exclusion Criteria

The exclusion criteria will be individuals with systemic, infectious, or inflammatory diseases or those taking medications, antibiotics, or fluoride in the last month; regular consumers of products and mouthwashes containing xylitol or sorbitol, with abnormal salivary flow (<1 ml/min), pregnant women or those on contraceptive pill treatment, or with eating disorders (anorexia and bulimia); subjects with periodontal disease or presence of dental caries.

• The variables described in this section should be consistent with those mentioned in (APPENDIX C) the table of operationalization of the variables

The variables of interest will be chewing gums, salivary flow level, and salivary pH during 4 time periods: initial (without chewing gums), at 10, 20, and 30 minutes after consuming the chewing gums.

Detailed and sequential description of all procedures that will be carried out to achieve each of the stated objectives. At least the following should be included.

7.1 Procedures: Students will be invited to participate through the study's presentation in each and every classroom of the students enrolled in the period September 2023-February 2024. At the end of the presentation, they will be invited to sign the informed consent, a document in which participants will provide their cell phone numbers so that they can be contacted via WhatsApp messages for the preliminary examination of their oral cavity to verify compliance with the inclusion criteria, as well as for sample

collection.

7.2 Sample Selection: Participants who meet the selection criteria will be probabilistically assigned using simple random sampling through a lottery system and will be assigned to each group. There will be 4 groups: the first group, G1, will consume chewing gums with 100% xylitol; the second group, G2, will consist of individuals who consume sugar-free chewing gums; the third group, G3, will consist of participants who chew sugared gums; and the fourth group, G4, will serve as the control group and will chew paraffin (Figure 2). This procedure will be carried out by investigator 1 (**Appendix D - Chewing Gum Information**)

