The principal investigator, investigator 1 and 2, and technician 1, as well as the participants who will form the different groups consuming the chewing gums, will be unaware of the type of gum (double-blind). Both the chewing gums and the paraffin will have the same weight (1.3 g), and the blinding method will involve the presence of identical, pre-numbered containers containing the different chewing gums. This information will only be accessible to technician 2. Saliva samples will be collected by the principal investigator, and the data will be recorded on a form specifically designed for this purpose by technician 1, which will be executed in the Molecular Biology laboratory (**Appendix E - Data Collection Form**).

7.3 Saliva Sample Collection: Saliva samples will be taken between 8 to 10 am, ensuring that subjects have not ingested food, smoked, or brushed their teeth at least 1 hour prior to sample collection. Participants will be asked to rinse their mouths with pure water to remove any food residue. Subsequently, they will be seated in a chair in an upright position with their head slightly tilted forward and eyes open, and the basal saliva sample will be taken as indicated by the established protocol for collecting unstimulated saliva by Tomas Seif. Before starting the test, participants will be asked to swallow saliva. They should keep their mouth slightly open and allow saliva to drain into the tube. The test will last five minutes, during which salivary pH will be evaluated and weighed, denoted as T1. For stimulated saliva, the protocol dictated by the Faculty of Dentistry at the University of Southern California will be used, utilizing the drainage method. Stimulated saliva will be collected in another pre-weighed test tube at three additional time intervals: T2 from 5 to 10 minutes, T3 from 15 to 20 minutes, and T4 from 25 to 30 minutes after the start of chewing gum consumption. Salivary flow and pH level measurements will be evaluated immediately using a pH meter (BT-675 meter, Boeco-Germany), performed by the principal investigator. Sample collection will be conducted over a period of two weeks.

Figure 2. Random allocation of participants for the determination of salivary flow and pH level. 7.4 Operation mechanism of the desktop pH meter BT-675 BOECO-Germany

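### Does the salivary-flow exclusion need rewriting because it names neither the type of saliva nor a measurement before the lottery?

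*Protocol*

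**What the plan says.** The Exclusion Criteria section of the protocol removes people "with abnormal salivary flow (<1 ml/min". It does not name the type of saliva, the collection method or the time of measurement.

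Section 7.1 describes one check before allocation. Volunteers are contacted "for the preliminary examination of their oral cavity to verify compliance with the inclusion criteria". The Inclusion Criteria section lists "participants with at least 20 teeth, providing written informed consent, and being willing to comply with the study procedures", with no flow item.

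Section 7.2 then states: "Participants who meet the selection criteria will be probabilistically assigned using simple random sampling through a lottery system".

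Saliva collection first appears in section 7.3. The unstimulated sample comes first: "The test will last five minutes, during which salivary pH will be evaluated and weighed, denoted as T1". Next, "Stimulated saliva will be collected in another pre-weighed test tube at three additional time intervals"; these are T2 to T4, timed from the start of chewing.

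**The concern.** The protocol treats unstimulated and stimulated saliva as separate measurements with separate collection methods, so a flow limit with no saliva type can be read in two ways, and the two readings may exclude different people.

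Timing adds to the doubt. Most of the other exclusions can be asked about or seen at an oral examination, whereas a rate in ml/min needs a timed collection. In the order of the text, the first such collection follows the lottery. If stimulated saliva is meant, the only stimulated collections described are T2 to T4, which are made with the assigned product and are themselves outcome measurements.

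Three things would be at stake: whether staff apply the rule in the same way to everyone, whether a low T1 found after the lottery removes someone already allocated, and whether the report can say who was eligible. Flow is also an outcome, so the limit helps to set the range of flow among those studied.

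**Working it through.** **1. The text, side by side**

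| Question | What the protocol gives |
|---|---|
| Must flow be known before allocation? | Yes. Section 7.2 admits only people who meet the selection criteria. |
| Does any section say flow is checked after allocation? | No. |
| Is a timed collection expressly placed before the lottery? | Not in the visible text. |
| Can a described collection serve for resting flow? | Yes. T1 precedes chewing. |
| Can a described collection serve for stimulated flow? | No. T2 to T4 follow the start of the assigned product. |

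The sections are silent on one point but do not conflict. That T1 follows the lottery is inferred from the section order (7.2, then 7.3); no time is given for the lottery.

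The reference to inclusion criteria in section 7.1 should not be pressed. The population definition also mentions inclusion criteria only, although the exclusions plainly apply. An oral examination is moreover the natural way to find caries and periodontal disease, which are both exclusions.

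**2. The plan's sample size**

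Inputs from the sample-size text: z-values 1.96 and 1.282, variance 1, difference 1, loss 15%.

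- n = 2 × (1.96 + 1.282)² × 1 / 1² = 21.02. The protocol prints 20.99 and uses 21.
- 21 / 0.85 = 24.7, which rounds up to 25 per group, as stated.

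The flow rule can reduce these numbers only if people are removed after allocation, which section 7.2 does not direct. As a hypothetical, take power = Φ(√(n/2) − 1.96), with difference and SD both 1:

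- n = 25: Φ(3.536 − 1.96) = 94%.
- n = 25 × 0.85 = 21.25: Φ(3.260 − 1.96) = 90%.
- A further 15% removed, n = 21.25 × 0.85 = 18.06: Φ(3.005 − 1.96) = 85%.

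The last line needs both an assumed 15% removal rate and a departure from section 7.2.

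**3. Can the share below the limit be estimated?**

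The only flow figures are the cited results in the Research Problem section: "there was a higher average at two minutes (1.89 \pm 0.42" and, at the other end, "which decreased to 1.04 \pm 0.31 at 30 minutes". The sentence is garbled, so assigning the second 1.89 (SD 0.45) to a second gum at two minutes is an interpretation. Assuming normality and ml/min:

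- Two minutes: Φ((1 − 1.89)/0.42) = 1.7%; Φ((1 − 1.89)/0.45) = 2.4%.
- Thirty minutes: Φ((1 − 1.09)/0.31) = 38.6%; Φ((1 − 1.04)/0.31) = 44.9%.

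Allocating 100 would mean screening 100/(1 − p) otherwise eligible students: 102, 103, 163 or 182, from 1275 enrolled.

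These numbers do not settle the matter. All four are post-gum values with no printed unit, from a study whose title says children. None describes resting flow, so they cannot give the cost of screening on T1. The documents contain no resting-flow distribution for adults aged 18 to 25.

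**4. Could a comparison between groups be biased?**

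A limit checked before the lottery acts on one common pool. If T1 were instead read after the lottery, it would still precede any chewing. Section 7.2 keeps the participants, the principal investigator and technician 1 unaware of the product. Either way the rule does not depend on group.

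**The case for a change.** The strongest case for a change is that eligibility rules and screening steps belong in a protocol and are not normally left to a statistical analysis plan. The form asks for procedures in sequence, so placing allocation in 7.2 and collection in 7.3 is more than layout. A definition of the flow variable in an appendix would not by itself supply a measurement before the lottery. Under the stimulated reading, nothing described can be used.

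Part of this stands. In the visible text the saliva type is missing and no timed collection is expressly placed before the lottery.

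It does not follow that the rule cannot be carried out. Under the resting reading, T1 is suitable and only its order relative to the lottery is unstated. Uneven application is also less likely than it seems, since section 7.3 has the principal investigator measure every sample in one laboratory. The resources table also lists technician 2, who holds the container code, as collecting samples, but it too assigns measurement to the principal investigator.

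Figure 2, cited in section 7.2 for the allocation, could show the sequence. Appendix C (variable definitions) and Appendix E (data collection form) could give the definition. None is in the public text, nor are some other pages. Under the stimulated reading, a remedy would add a collection for every person screened, with no demonstrable gain for the comparison.

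**Conclusion.** No change follows. The observation about the wording is accurate, but it concerns an undefined term and an unwritten step. It is not an error or a contradiction. The investigators can settle which saliva the limit refers to and when it is checked while keeping to section 7.2, and can report what they did.

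No bias between groups or inflation of the error rate can be shown. Power is untouched if eligibility is settled before the lottery, as section 7.2 requires. The fall from 90% to 85% arises only under an assumed 15% removal after allocation, on top of the planned loss. The proportion of students affected cannot be computed from the documents.

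This rests on three assumptions: that section 7.2 is followed, that one reading of the limit is used for everyone, and that the material not shown does not say otherwise. What remains is a minor point of wording about who enters the study, with no shown consequence for the comparison of the four groups.

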7.7 Information Management: Technician 1 will handle the physical documents until the laboratory process is completed. Subsequently, Technician 1 will provide the data matrix in Excel for further analysis by Investigator 1. Participants will not receive individual research results; instead, the final research results will be disseminated.

8. Human biological samples do not require exportation as they will be disposed of immediately after the determination of salivary flow and pH level.

9. Data Analysis Plan

The data analysis will be conducted using SPSS v.25. Descriptive analysis of the data will be performed. Chi-square test will be used for demographic data, Levene's test will determine the homogeneity of the data, and ANOVA test will be used to determine differences in means. Post-hoc Tukey's test will be employed to find significant differences between the means of the groups, with a significance level set at p<0.05. All analyses will be conducted by Investigator 1.

HUMAN AND MATERIAL RESOURCES

1. Enumerate the human resources that will participate in the research, detailing the functions each one will fulfill; it should coincide with the section.

1. Principal Investigator		Collecting the sample and measuring salivary flow and pH		
2. Investigator 1	Inviting participation via email and conducting statistical analysis			
3. Investigator 2	Sending study participation information via email.			
4. Technician 1		Collecting quantitative data on the data sheets.		
5. Technician 2		Collecting the sample.		

2. Provide a detailed description of all the material resources used for the execution of the project, including necessary information

Among the materials are nitrile gloves, masks, Falcon tubes, funnel, hand towels, xylitol chewing gums, Trident, Agogo, and paraffin. As for the equipment, a pH meter and a precision scale (Boeco) are needed.

ETHICAL AND GENDER CONSIDERATIONS

1. Provide a detailed description of the measures to be taken to ensure the rights of individuals to minimal risk, autonomy, and confidentiality

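### As written, investigator 1 draws participants into product-defined groups, is listed as blinded and runs every analysis, so the stated blind does not hold for the person who allocates and analyses

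*Protocol*

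**What the plan says.** Under Research Design the protocol calls the trial double-blind. Four statements then bear on investigator 1.

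- **Allocation (7.2 Sample Selection).** Eligible participants are "probabilistically assigned using simple random sampling through a lottery system and will be assigned to each group". The groups are named by product: "the first group, G1, will consume chewing gums with 100% xylitol", with G2 the sugar-free gum, G3 the sugared gum and G4 paraffin. The paragraph ends: "This procedure will be carried out by investigator 1".
- **Blinding (next paragraph of 7.2).** The staff who are not to know the gum are "The principal investigator, investigator 1 and 2, and technician 1", along with the participants. As to method, "the blinding method will involve the presence of identical, pre-numbered containers containing the different chewing gums", and only technician 2 has access to that information.
- **Analysis (9. Data Analysis Plan).** "All analyses will be conducted by Investigator 1".
- **Roles (Human and Material Resources).** Investigator 1's entry reads "Inviting participation via email and conducting statistical analysis". Running the lottery is not listed there. Technician 2 is listed as collecting the sample, although the blinding paragraph gives saliva collection to the principal investigator.

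**The concern.** Group labels that the protocol itself ties to products are not masked codes. A person who draws someone into G1, and knows the protocol, knows that this participant gets the xylitol gum. That person is then said to be blinded and is the only analyst. If the text is followed literally, the report could not truthfully say that investigator 1 was blinded or that the analysis was. Decisions left open at the analysis stage, such as how to treat an outlying value, would be made by someone who knows which arm is xylitol. Knowledge gained at the draw cannot be undone, so the matter has to be settled before the first allocation.

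**Working it through.** No figure in the protocol is in dispute, so the check sets the role statements side by side.

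1. **Who allocates?** Investigator 1 (7.2).
2. **To what?** To G1–G4, each defined by product in the same paragraph. Container numbers are not mentioned at this step.
3. **Who is said not to know the product?** Investigator 1, among others (blinding paragraph of 7.2).
4. **Can 1 to 3 all hold?** Only if the lottery slip carries something that investigator 1 cannot translate into a product, such as a container number or a neutral code. The numbered containers and technician 2's key make this possible, but the text does not connect the draw to the containers. It also does not say who turns a drawn group into the right container. As written, the statements conflict.
5. **Does the knowledge reach the results?** Yes. Section 9 gives investigator 1 every analysis, and the text does not say that the analysis file carries masked labels.
6. **Does it reach the measurements?** Not through this conflict. The principal investigator collects the saliva and measures flow and pH (7.2 and 7.3). The pH meter locks its reading (7.4), and samples are discarded straight after measurement (7.5).
7. **Does it let investigator 1 steer who enters which arm?** This is not shown. Consent and the oral examination come before the draw (7.1, 7.2), and a fair draw does not reveal the next assignment.
8. **Does investigator 1 handle the data sheets?** The protocol is inconsistent. Section 7.6 first says that only investigator 1 has access to the storage space and builds the Excel matrix, then says that only technician 1 has access. Section 7.7 has technician 1 hold the documents and supply the matrix.

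**Reach.** Planned allocations: 4 groups × 25 = 100. Post-chewing results analysed by investigator 1: 2 outcomes × 3 times (T2, T3, T4) = 6. These count what the conflict touches; they do not measure bias.

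**The case against.** The strongest reply is that 7.2 describes the arms for the reader and the next paragraph supplies the mechanism. On that reading, investigator 1 draws people into coded groups and only technician 2 knows what each container holds. Figure 2 and the data form in Appendix E, neither of which is in the text available here, might show such coding. Masked arm letters and the timing of key release are also matters that a statistical analysis plan often settles.

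Part of this stands. The containers could preserve the blind, so the right wording is that it does not hold as written, not that it must fail in practice. The plan also limits the analyst's freedom by naming ANOVA with Tukey comparisons. But the protocol itself fixes who allocates, who is blinded and who analyses, and its text does not make those three statements compatible. That is a conflict in what is stated, not a detail left for later.

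A reader might infer more than the documents support:

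- **That the whole double-blind collapses.** This conflict does not unblind the participants or the principal investigator.
- **That allocation is biased.** Eligibility is settled before the draw. Knowing an arm after the draw is not the same as foreseeing it.
- **That investigator 1 could influence repeat readings.** None are provided for, and the samples are discarded at once.
- **That investigator 1 certainly has access to the data sheets.** Sections 7.6 and 7.7 conflict on this.

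**Conclusion.** The point holds in a limited form. As the protocol is written, the blind is not secured for investigator 1, who both allocates and analyses. The main exposure is an unblinded analysis of the six post-chewing results; outcome measurement is not affected by this conflict. No bias can be quantified from the document.

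The conclusion assumes that the lottery works as 7.2 describes it, with draws into G1–G4, and that the missing figure and appendices do not specify a coded draw. If they do, the correction is to say so in 7.2. Because double-blind is the stated design and the repair is only fully effective before the first draw, it should be made before enrolment starts.

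**What to change.** 1. **7.2, allocation.** State that investigator 1 draws only a container number and never a group label. Technician 2 prepares the containers and holds the number-to-product key.
2. **Technician 2's role.** The key holder takes no part in saliva collection. Amend the role table to agree with 7.2, which gives collection to the principal investigator. Without this, the fix would leave the key with someone listed as collecting samples. Add the lottery to investigator 1's entry.
3. **Data form and Excel matrix.** Carry only the container number or neutral arm letters A–D.
4. **Section 9.** Release the product key to investigator 1 only after the data are closed and the ANOVA and Tukey tests have been run on the coded arms.
5. **7.6 and 7.7.** State once who has access to the data sheets and who builds the matrix.

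If this is not done, do not describe investigator 1 or the analysis as blinded.

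The cost is some rewording, with no extra staff or visits, since the containers and the key holder are already planned. The small downside is that the lottery slips must carry container numbers and the key must be held back until the analysis is done.
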